Grade 3 AEs (related, first event)	
 
Hold dose of ivosidenib until resolution to Grade 1 or baseline within 28 days of supportive therapy and then resume dose.
 
Manage with supportive therapy according to the institutional standard of care.
 

	
 
If the Grade 3 AE recurs (a second time), consider reducing ivosidenib to 250 mg. Re-escalation may be permitted after discussion with the Lead Investigator.
 

	
 
If the Grade 3 AE recurs (a third time) despite dose reduction of ivosidenib, then consider discontinuing ivosidenib in consultation with the Lead Investigator.
 

Grade 4 AEs (related, first event)	
 
Hold ivosidenib
 
Manage with supportive therapy according to the institutional standard of care.
 
If the AE resolves to Grade 1 or baseline within 28 days, then restart ivosidenib dosing at 250 mg in consultation with the Lead Investigator.
 
If the AE does not resolve to Grade 1 or baseline within 28 days, consider discontinuing study treatment in consultation with the Lead Investigator.
 
If the Grade 4 AE recurs (a second time), despite dose reduction, ivosidenib should be discontinued in consultation with the Lead Investigator.
 

\*See Table 2 for specific dose modifications for QTcF prolongation.

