### Non-hematologic AEs:

- Grade 3 or 4 nausea or vomiting:
  - o If no anti-emetic prophylaxis was administered, Grade 3 or 4 nausea or vomiting is considered a DLT only if lasting> 3 days despite maximum supportive care.
  - o Grade 3 or 4 nausea or vomiting despite anti-emetic prophylaxis of any duration will be considered a DLT.
- Grade 3 or 4 diarrhea:
  - o If no anti-diarrheals were administered, Grade 3 or 4 diarrhea is considered a DLT only if lasting> 3 days despite maximum supportive care.
  - o Grade 3 or 4 diarrhea despite the administration of anti-diarrheals of any duration will be considered a DLT.
- Any other Grade 3 or 4 non-hematological AE, with the exception of asymptomatic amylase/lipase or other biochemical marker that does not resolve with adequate treatment and/or within a week.

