### General:

- Interruption of ivosidenib dosing for more than a total of 2 weeks (not necessarily consecutive) during Cycle 1, if due to AEs related to ivosidenib.
- Delay of starting Cycle 2 for> 2 weeks, if due to AEs related to ivosidenib.

All safety data in Cycle 1 and subsequent cycles will be monitored on an ongoing basis.

A patient who experiences a DLT at any dose level will receive appropriate treatment and supportive

care as necessary and will be monitored closely until resolution of the AE to Grade Oto 1 severity or Baseline severity, whichever is more abnormal, or until the AE is stabilized at any acceptable grade.

Patients who experience a DLT but who, in the opinion of the Investigator, are deriving clinical benefit will be permitted to continue treatment with ivosidenib at a lower dose that has been demonstrated to be well tolerated upon reasonable resolution of the DLT.

AEs will be tabulated by type, severity, and attribution. Immune responses, as assessed at baseline, post ivosidenib lead in, and week 9 (first restaging) will be analyzed by mixed effects regression for longitudinal data. Baseline and post-treatment values will also be compared between responders and non-responders.

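### For a first related Grade 3 AE that is a DLT on ivosidenib 500 mg, Table 1 by default resumes the dose, while Section 7.5 describes continuation only at a lower dose; neither cites the other

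*Combined protocol and SAP*

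**What the plan says.** Section 5.5.1.1, Table 1, first related Grade 3 event: "Hold dose of ivosidenib until resolution to Grade 1 or baseline within 28 days of supportive therapy and then resume dose". The row names no restart dose. For recurrence it says "If the Grade 3 AE recurs (a second time), consider reducing ivosidenib to 250 mg", and then "Re-escalation may be permitted after discussion with the Lead Investigator". For a first related Grade 4 event that resolves within 28 days, the instruction is "then restart ivosidenib dosing at 250 mg in consultation with the Lead Investigator".

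Section 7.5 defines a DLT as a Cycle 1 event meeting any of several criteria. They include "Any other Grade 3 or 4 non-hematological AE", with an exception for asymptomatic amylase, lipase or other biochemical changes. They also include "Interruption of ivosidenib dosing for more than a total of 2 weeks (not necessarily consecutive) during Cycle 1", and a delay of more than 2 weeks in starting Cycle 2, in both cases when caused by ivosidenib-related AEs. After a DLT at any dose level, participants who in the investigator's opinion "are deriving clinical benefit will be permitted to continue treatment with ivosidenib at a lower dose that has been demonstrated to be well tolerated" may do so once the DLT has reasonably resolved.

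Section 5.5.1.1 points to Section 5.9, Table 1 and Table 2, but not to Section 7.5. Section 7.5 does not point to Section 5.5.1.1 or Table 1, and Table 1 has no row or exception for DLTs.

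**The concern.** Table 1 is where a treating investigator looks for a restart dose, and it does not separate a dose-limiting Grade 3 event from any other. Section 7.5 does make that separation and leads to a different dose. For the same participant, one section leads back to 500 mg and the other to a lower dose.

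What is at stake is individual safety. A participant whose first cycle on 500 mg produced a DLT could be put back on 500 mg by someone who read only the dose-modification table. Two centers enroll, so handling of the same event could also differ between them.

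**Working it through.** No plan figure needs reproducing to settle this. The check sets the rules side by side, then asks what size can be stated.

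**1. Do the two rules cover the same events?** Table 1 covers related Grade 3 events in any cycle. Section 7.5 covers Cycle 1 events meeting its criteria, including most Grade 3 non-hematological events. A first, related Grade 3 event in Cycle 1 that meets a DLT criterion falls under both.

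**2. What dose does the Grade 3 row mean?** Section 5.5.1.1 allows only one reduction, from 500 mg to 250 mg, and nothing lower. If the first restart were already at 250 mg, considering a cut to 250 mg at recurrence would be empty. The Grade 4 row also names 250 mg where that is intended. So the Grade 3 restart is at the prior dose.

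**3. Side by side, for a DLT on 500 mg**

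| | Table 1, first related Grade 3 | Section 7.5, after a DLT |
|---|---|---|
| Restart dose | Prior dose, 500 mg | Lower dose, which can only be 250 mg |
| Condition | Resolution to Grade 1 or baseline within 28 days | Judged clinical benefit and reasonable resolution |
| Refers to the other section | No | No |

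**4. Can following Table 1 itself create the DLT?** Table 1 allows a hold of up to 28 days.
- Interruption criterion: a hold from Day d through Day 28 misses 28 − d + 1 = 29 − d days. For d = 14 this is 15 days, more than 14, so a DLT. For d = 15 it is 14 days, which is not.
- Cycle 2 delay criterion: assume Cycle 2 waits for ivosidenib and the full 28 days are used. Dosing restarts on Day d + 28 against a planned Day 29, a delay of d − 1 days. For d = 20 that is 19 days, also a DLT.

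**5. Which events already have their own rule?**
- QTcF prolongation: the Table 1 footnote says "See Table 2 for specific dose modifications for QTcF prolongation", and Table 2 resumes at 250 mg after Grade 3.
- Confirmed PML or Guillain-Barre syndrome: ivosidenib stops permanently (Sections 7.2.4.2 and 7.2.4.3).
- Events attributed to nivolumab: ivosidenib may continue after consultation with the PI (Section 5.5.1.1).
- More than one AE requiring modification: reduce to 250 mg (Section 5.5.1.1).

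The conflict is confined to what remains.

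**6. How many participants?** The documents do not give the share of DLTs in scope. They allow only an expected count of all DLTs, n × rate. The prior mean in Section 8.3 is 1/(1 + 4) = 0.2; rates of 0.1 and 0.3 are assumptions.

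| Assumed DLT rate | n = 35 | n = 18 (stop after stage 1) |
|---|---|---|
| 0.1 | 3.5 | 1.8 |
| 0.2 | 7.0 | 3.6 |
| 0.3 | 10.5 | 5.4 |

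These are expectations for DLTs of every kind, ignoring any pause under the DLT rule. They are not a ceiling, and the in-scope number is an unknown part of the DLTs that occur.

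**The case against.** The best case on the other side has four parts.

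- **Both readings are inferred.** Section 7.5 does not contain the word only, and the Grade 3 row does not say same dose, whereas the Grade 2 nausea and vomiting row does allow resumption at the same dose. This stands as a caution. But a lower dose is the only continuation Section 7.5 describes, and the recurrence line makes sense only if the first restart is at the prior dose. If the Grade 3 row were instead judged silent, it would give no restart dose after a DLT, which calls for the same repair.
- **The sections can be followed together.** Section 7.5 is the more specific rule, and Section 5.5.1.1 lets the investigator modify ivosidenib for any AE. Choosing 250 mg for a participant judged to be benefiting satisfies both. This stands: the clash is between defaults and is not a logical impossibility. The discretion is permissive, however, and nothing in Table 1 tells the reader that a DLT calls for a lower dose.
- **Compliance.** A reader might infer that two centers could restart at different doses while each complies with the protocol. The documents do not support that. A site restarting 500 mg after a DLT would follow Table 1 but depart from Section 7.5.
- **Rarity.** No DLTs were reported in the single-agent solid-tumor study (Sections 1.4.3.1 and 1.5; 168 participants in the latter). This stands as a reason to expect few cases, although that study did not include nivolumab.

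**Conclusion.** The point holds for a first, related Grade 3 AE in Cycle 1 on 500 mg that meets the DLT definition and has no event-specific rule. Table 1 used alone restarts the dose on which the DLT occurred, contrary to Section 7.5. The conclusion rests on reading the Grade 3 restart as the prior dose and Section 7.5 as allowing only the continuation it describes. Both are inferences well supported by the text.

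The number affected is unknown and may be small; the expected counts of all DLTs give context only.

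A reader might infer that the statistical design is compromised. It is not: a DLT is counted when it occurs, before any restart, so the stopping table in Section 8.2.4 is unaffected, and the Simon boundaries do not depend on the restart dose. The case for a change is participant safety. It is worth making because the wording can be corrected at almost no cost.

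**What to change.** Make Section 7.5 govern DLTs and link the two sections.

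1. Footnote to the Table 1 Grade 3 row: *If the event meets the DLT definition in Section 7.5, Section 7.5 governs: a participant on 500 mg who is judged to be deriving clinical benefit may restart only at 250 mg after resolution, in consultation with the Lead Investigator. QTcF prolongation follows Table 2; PML and Guillain-Barre syndrome follow Section 7.2.4.*
2. In Section 7.5, replace the unspecified lower dose with: *250 mg if the DLT occurred on 500 mg (see Table 1); if it occurred on 250 mg no lower dose is available, so same-dose restart is not automatic and the case goes to the Lead Investigator.*

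The dose-level limit is needed because Section 7.5 applies at any dose level and Dose Level -1 is already 250 mg; an unqualified 250 mg rule would return a participant with a DLT on 250 mg to that dose. The clinical-benefit condition appears in the footnote so that the two sections match. Do not add a re-escalation allowance for DLTs.

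The cost is wording in two sections, with no added visits or participants and no change to the design. The downside is that a few participants restart at 250 mg instead of 500 mg. Section 3.2.1 tempers this: plasma 2-HG fell at all doses with no apparent dose response, although 500 mg was the dose chosen for expansion.

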# 5.5.2 Continuation of Treatment beyond Radiographic Progression

Accumulating evidence indicates that a minority of participants treated with immunotherapy may derive clinical benefit despite initial evidence of PD.

- Participants will be permitted to continue treatment beyond initial RECIST Version 1.1 (solid tumors) or Response Assessment in Neuro-Oncology (RANO) (gliomas)-defined PD, assessed by the investigator, if they meet the following criteria:
- Investigator-assessed clinical benefit
- Tolerance of study drug
- Stable performance status
- Treatment beyond progression will not delay an imminent intervention to prevent serious complications of PD (e.g., CNS metastases).

A radiographic assessment/scan should be performed within 6 weeks of initial investigator-assessed progression to determine whether there has been a decrease in the tumor size or continued PD. The assessment of clinical benefit should be balanced by clinical judgment as to whether the participant is clinically deteriorating and unlikely to receive any benefit from continued treatment.

If the treating investigator deems that the participant continues to achieve clinical benefit by continuing treatment, the participant should remain on the study and continue to receive monitoring according to the study schedule.

For the participants who continue study treatment beyond progression, further progression is defined as an additional 10% increase in tumor burden with a minimum 5 mm absolute increase from time of initial PD. This includes an increase in the sum of diameters of all target lesions and/or the diameters of new measurable lesions compared to the time of initial PD. Treatment should be discontinued permanently upon documentation of further progression.

New lesions are considered measurable at the time of initial progression if the longest diameter is at least 10 mm (except for pathological LNs, which must have a short axis of at least 15 mm). Any new lesion considered non-measurable at the time of initial progression may become measurable and, therefore, included in the tumor burden if the longest diameter increases to at least 10 mm (except for pathological LNs, which must have a short axis of at least 10 mm (except for pathological LNs, which must have a short axis of at least 15 mm). In situations where the relative increase in total tumor burden by 10% is solely due to inclusion of new lesions, which become measurable, these new lesions must demonstrate an absolute increase of at least 5 mm.

# 5.6 Guidelines for Management of QT Prolongation

The following are guidelines for the management of AEs of special interest based on the ivosidenib nonclinical and clinical safety findings in participants with solid tumors to date.

Prolongation of QTcF interval has been observed in monkeys at relatively high doses of ivosidenib (see Section 7.2.7.1) and has been identified as an expected risk of treatment with ivosidenib (see the Investigator's Brochure, Version 7.0). Cumulatively, QT prolongation has been experienced by 37 (17%) of the 223 participants in Study AG120-C-001 (8 participants [4%] had SAEs) and by 17 (10%) of the 168 participants in Study AG120-C-002 (no SAEs reported). There has been one report of QT prolongation in Study AG120-221-C-001, as of April 18, 2017.

Participants may be at increased risk for the development of QT prolongation when treated with ivosidenib in combination with fluoroquinolones, azole antifungal agents, or serotonin (5-HT3)

antagonists. Investigators need to be vigilant; refrain from administering concomitant medications associated with QT prolongation and if no other therapeutic options are available, monitor participants receiving study treatment with the combination of these drugs, and evaluate ECG and electrolytes (including potassium, magnesium, and calcium) particularly in participants presenting with nausea, vomiting, or diarrhea.

Participants who experience prolongation of the QTcF interval to> 480 ms (CTCAE Grade;::: 2} while receiving study treatment, should be promptly evaluated for causality of the QTcF prolongation and managed according to the following guidelines and Table 2:

- Levels of electrolytes (potassium, calcium, and magnesium) should be checked and supplementation given to correct any values outside the normal range.
- Concomitant therapies should be reviewed and adjusted as appropriate for medications with known QT prolonging effects.
- If no other cause is identified and the treating investigator believes it is appropriate, particularly if QTcF remains elevated (after above measures have been implemented, or as determined by the Investigator}, study treatment may be interrupted, and an ECG should be rechecked in approximately 1 week after the QTcF prolongation was first observed or more frequently as clinically indicated. If QTcF has recovered or improved and the Investigator believes it is safe to do so, re-challenge with study treatment should be considered if held.
- ECGs should be conducted at least weekly (eg, at every scheduled visit) for 2 weeks following QTcF reduction 480 ms.

Participants who experience prolongation of the QTcF interval to> 500 ms (CTCAE Grade;::: 3} while receiving study treatment, should be promptly evaluated for causality of the QTcF prolongation and managed according to the following guidelines and Table 2:

- Levels of electrolytes (potassium, calcium, and magnesium) should be checked and supplementation given to correct any values outside the normal range.
- Concomitant therapies should be reviewed and adjusted as appropriate for medications with known QT prolonging effects.
- If no other cause is identified and the treating investigator believes it is appropriate, particularly if QTcF remains elevated (after above measures have been implemented, or as determined by the Investigator}, study treatment may be interrupted, and an ECG should be rechecked in approximately 1 week after the QTcF prolongation was first observed or more frequently as clinically indicated. If QTcF has recovered or improved and the Investigator believes it is safe to do so, re-challenge with study treatment should be considered if held.
- ECGs should be conducted at least weekly (eg, at every scheduled visit) for 2 weeks following QTcF reduction 480 ms.

CTCAE Grade	Management
Grade 2 (QTcF > 480 and :5 500 ms)	• The dose of study treatment may be reduced to 250 mg QD without interruption of dosing. The dose of study treatment may be re-escalated to the prior dose in 14 days after QT prolongation has decreased to :5Grade 1.
Grade 3 (QTcF > 500 ms on at least two separate ECGs)	
 
Hospitalization for continuous cardiac monitoring and evaluation by a cardiologist should both be considered.
 

	
 
Dosing with study treatment will be interrupted. If QTcF returns to within 30 ms of baseline or< 450 ms for males and< 470 ms for females within 14 days, treatment may be resumed at a reduced dose of 250 mg.
 

	
 
The dose of study treatment cannot be re-escalated following dose reduction for Grade 3 QTcF prolongation unless the prolongation was associated with an electrolyte abnormality or concomitant medication.
 

Grade 4 (QTcF > 500 ms or> 60 ms change from baseline with Torsades de pointes or polymorphic ventricular tachycardia or signs/symptoms of serious arrhythmia)	
 
Participants should be admitted to a hospital for continuous cardiac monitoring and discharged only after review by a cardiologist.
 
Dosing with study treatment should be permanently discontinued.
 

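### Section 5.6: the bullets for QTcF above 500 ms repeat those for above 480 ms and are inconsistent with Table 2 for confirmed Grade 3 prolongation (minor, patient safety)

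*Combined protocol and SAP*

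**What the plan says.** Section 5.6 has two bullet blocks, one for QTcF above 480 ms and one for QTcF above 500 ms. The lead-in to the second says that participants "should be promptly evaluated for causality of the QTcF prolongation and managed according to the following guidelines and Table 2".

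The bullet on interruption in that block opens with a condition, "If no other cause is identified and the treating investigator believes it is appropriate", and continues that "study treatment may be interrupted, and an ECG should be rechecked in approximately 1 week after the QTcF prolongation was first observed", or more often if clinically indicated. On restart it says: "If QTcF has recovered or improved and the Investigator believes it is safe to do so, re-challenge with study treatment should be considered".

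Table 2 then sets management by grade. Its Grade 3 row applies to a QTcF above "500 ms on at least two separate ECGs". The instruction is "Dosing with study treatment will be interrupted". If QTcF comes back to within 30 ms of baseline, or below 450 ms (males) or 470 ms (females), within 14 days, "treatment may be resumed at a reduced dose of 250 mg". Re-escalation is barred "unless the prolongation was associated with an electrolyte abnormality or concomitant medication".

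Three other places bear on the point:

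- Section 5.5.1.1: Table 1 tells sites to hold ivosidenib for a first related Grade 3 event until it resolves to Grade 1 or baseline. The Table 1 footnote refers QTcF dose changes to Table 2.
- Section 7.2.4.1 covers QTcF above 480 ms, labelled Grade 2 as printed. It defers to the Investigator's Brochure for details and allows ivosidenib to be restarted after clinical improvement.
- Section 6.4.2 refers to section 5.7 for QT management. Section 5.7 is about infusion reactions.

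**The concern.** QT prolongation is named in section 5.6 as an expected risk of ivosidenib. The bullets for the more dangerous range are a word-for-word repeat of those for the milder range, so they carry the milder instructions. A clinician who works from the bullets alone could keep a participant with confirmed Grade 3 prolongation on drug because another cause was found. The same clinician could re-challenge on partial improvement. Table 2 allows neither. Two safety rules for the same event should not differ on whether to stop the drug or on when to restart it.

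**Working it through.** The plan states no figure for this point, so the check is mainly a comparison of texts for one event: Grade 3 prolongation confirmed on at least two ECGs.

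| Question | Bullets for QTcF above 500 ms | Table 2, Grade 3 |
|---|---|---|
| Is dosing interrupted? | Optional, at the investigator's judgment | Mandatory |
| Does another cause matter? | Yes; the option to hold is written only for the case with no other cause | No; an electrolyte or concomitant-drug cause relaxes only the bar on re-escalation |
| QTcF level for restart | None; recovery or improvement is enough if judged safe | Within 30 ms of baseline, or below 450 ms (males) / 470 ms (females) |
| Time limit for recovery | None | 14 days |
| Restart dose | Not stated | 250 mg |

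**Interruption.** Suppose a low potassium value is found and corrected. The bullets then call for no hold. Table 2 still does, because its exception for such a cause appears only in the re-escalation sentence.

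**Restart, with assumed values.** A male participant has a baseline QTcF of 430 ms and a confirmed reading of 510 ms, which falls to 490 ms.

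- Table 2 limits: 430 + 30 = 460 ms, or below 450 ms.
- 490 − 460 = 30 ms too high on the first; 490 − 450 = 40 ms too high on the second. Table 2 gives no restart.
- The bullet asks only for improvement (510 to 490 ms) and a judgment of safety. Re-challenge is then to be considered.

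**How many participants.** The Grade 3 QT rate is not given. Section 5.6 reports QT prolongation of any grade in 17 (10%) of 168 participants in the solid-tumor study, with no SAEs. Section 1.5 names the Grade 3 events seen in more than 2 of 168 participants, and QT prolongation is not among them. Assuming that list is complete, the ceiling is 2 cases:

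- 2/168 = 1.19%; 35 × 0.0119 = 0.42 cases.
- Clopper-Pearson upper 95% limit for 2/168 = 4.23%; 35 × 0.0423 = 1.48 cases.

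These are events arising, not events mismanaged, which would be fewer.

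**The case against.** The best defence is that the two texts are cumulative. The lead-in joins the bullets and Table 2, so an optional general instruction leaves the mandatory specific one in force, and a site that follows Table 2 breaches no bullet. The Table 1 footnote points the same way. Table 1 is also a second safeguard for a related event: in the example above, 490 ms is still Grade 2 and above baseline, so Table 1 would not release the hold either, although Table 1 alone would not impose 250 mg at a first event. All of this stands, and it is why the point is minor.

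A further defence is that the bullets apply from a single reading above 500 ms, while the Table 2 row needs two ECGs, so the optional wording may be meant for the unconfirmed stage. That is a fair guess at intent. But the block is labelled Grade 3 or higher, does not limit itself to unconfirmed readings, and runs on to re-challenge. The inconsistency in the text remains.

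Two stronger readings are tempting and are not supported:

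- *The protocol allows continued dosing or a full-dose restart in confirmed Grade 3.* The bullets are silent on dose, and Table 2, which the lead-in brings in, supplies both the hold and 250 mg.
- *Section 7.2.4.1 is a second conflict.* It is printed as Grade 2, for which Table 2 sets no mandatory hold and no QTcF limit for restart. It is silent on dose and threshold, and it defers to a brochure not available here.

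**Conclusion.** The interruption and re-challenge bullet for QTcF above 500 ms is inconsistent with Table 2 for confirmed Grade 3 on two matters: whether dosing must stop, and the conditions for restart. That is an error of wording in a safety rule, and it is minor. The comparison rests on the printed text alone. The expected count (about 0.4 in 35, about 1.5 at the upper limit) rests on the section 1.5 list being complete and on similar risk with the combination.

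A reader might also infer a gap for Grade 4 or a distortion of the toxicity rule. Neither follows. Section 4.4.1 and Table 2 both require discontinuation at Grade 4. Section 7.5 counts a Grade 3 or 4 non-hematologic event in Cycle 1 by its grade, so a DLT does not depend on which dosing text the site followed. Nothing here bears on sample size or the primary analysis.

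**What to change.** In the block for QTcF above 500 ms in section 5.6, replace the optional interruption and re-challenge bullet with: *For QTcF > 500 ms confirmed on at least two ECGs, interrupt, resume or permanently discontinue study treatment according to Table 2.*

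As tidying only:

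- Add *subject to Table 2* to the restart sentence in section 7.2.4.1. This is a clarification and does not correct a shown conflict.
- Change the cross-reference in section 6.4.2 from 5.7 to 5.6.

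The sponsor may also wish to ask for an earlier repeat ECG after a single reading above 500 ms. That is optional.

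The cost is protocol wording in three places. No procedure need be added, and neither sample size nor analysis changes.

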# 7.2.4.1 QT Prolongation

Prolongation of heart-rate corrected QT (QTc) interval has been observed in monkeys at relatively high doses of ivosidenib as well as in patients while receiving ivosidenib. Please refer to the current ivosidenib 1B for detailed information.

Participants may be at increased risk for the development of QT prolongation when treated with ivosidenib in combination with fluoroquinolones, azole antifungal agents, or serotonin (S-HT3) antagonists. Investigators need to be vigilant regarding concomitant medications associated with QT

prolongation, and if no other therapeutic options are available, monitor participants receiving AG-120 with the combination of these drugs, and evaluate ECG and electrolytes (including potassium, magnesium, and calcium) particularly in participants presenting with nausea, vomiting, or diarrhea.

Participants who experience prolongation of the heart-rate corrected QT interval, Fridericia's correction (QTcF) to> 480 ms (Grade 2) while treated with ivosidenib, should be promptly evaluated for causality of the QTc prolongation and managed according. For details, refer to the current Investigator brochure. Once the signs and symptoms resolve and the participant's clinical condition improves, ivosidenib may be reinitiated.

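### In the Grade 3 row of the QT management table (Section 5.6, Table 2), the baseline-relative limit for resuming ivosidenib has no absolute cap, so for baselines of 471–479 ms it lies above the 500 ms hold level

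*Combined protocol and SAP*

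**What the plan says.** Table 2 in Section 5.6 grades QTcF prolongation and sets an action for each grade.

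- **Grade 2** (above 480 ms, up to 500 ms): "The dose of study treatment may be reduced to 250 mg QD without interruption of dosing".
- **Grade 3 trigger:** "QTcF > 500 ms on at least two separate ECGs".
- **Grade 3 action:** "Dosing with study treatment will be interrupted. If QTcF returns to within 30 ms of baseline", or alternatively to below 450 ms for males or 470 ms for females, "within 14 days, treatment may be resumed at a reduced dose of 250 mg". Re-escalation is ruled out unless an electrolyte abnormality or a concomitant drug was involved. The row adds: "Hospitalization for continuous cardiac monitoring and evaluation by a cardiologist should both be considered".
- **Grade 4:** permanent discontinuation.

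The sex-specific limits are joined by *or*. They are a second route to resumption and do not cap the first.

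Exclusion 19 in Section 4.2 bars a baseline QTcF of 480 ms or more (the comparison sign is garbled in the extracted text and is read here as ≥). It also lets the PI approve a prolonged QTcF, with no stated upper bound.

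**The concern.** A release criterion should lie outside the range that triggers the hold. Here the hold level is fixed at 500 ms, while one route to release moves with the participant's baseline. For a long enough baseline the moving limit passes the fixed one, and the row does not say which then governs. Two sites could handle the same tracing differently and both cite the same row.

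The protocol names QT prolongation as an expected risk of ivosidenib, so the rule will be used. What is at stake is consistent handling of a few participants with long baselines. No endpoint, sample size or stopping boundary depends on it.

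**Working it through.** **Inputs**

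- Hold level: QTcF > 500 ms on at least two ECGs (Table 2, Grade 3).
- Relative release limit: baseline + 30 ms (same row).
- Eligible baselines: up to 479 ms in whole milliseconds without PI approval; higher with it (Section 4.2, exclusion 19).

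**Release limit = baseline + 30; overlap = limit − 500 where positive**

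| Baseline (ms) | Release limit (ms) | Overlap (ms) |
|---|---|---|
| 450 | 480 | none |
| 470 | 500 | none |
| 471 | 501 | 1 |
| 475 | 505 | 5 |
| 479 | 509 | 9 |
| 480 (PI-approved) | 510 | 10 |
| 490 (PI-approved) | 520 | 20 |

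Reading *within 30 ms* strictly (less than 30) shifts this by 1 ms: baselines of 472–479 ms then release at up to 501–508 ms.

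**Example.** Baseline 475 ms, two ECGs at 503 ms. Both exceed 500, so dosing is interrupted. But 503 − 475 = 28 ms, so the same values also meet the relative release limit.

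**Does another text cap the limit?**

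- The Section 5.6 text for QTcF above 500 ms sets this condition for re-challenge: "If QTcF has recovered or improved and the Investigator believes it is safe to do so". It gives no value.
- The 480 ms figure in the Section 5.6 ECG bullet governs how often follow-up ECGs are done, not restart.
- Table 1 (Section 5.5.1) asks for resolution to Grade 1 or baseline, but its footnote sends QTcF to Table 2.
- Section 7.2.4.1 requires signs and symptoms to resolve; once the "clinical condition improves, ivosidenib may be reinitiated". It gives no value. It also says "For details, refer to the current Investigator brochure", and the Brochure is not available to check.
- Section 7.5 makes most Grade 3 non-hematologic events in Cycle 1 a DLT. It lets participants who are benefiting continue at a lower dose once the DLT has reasonably resolved. It gives no value.

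**How many people?** The documents give no distribution of baseline QTcF.

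- Assumption: 1% to 10% of the 35 participants have a baseline above 470 ms. 0.01 × 35 = 0.35; 0.10 × 35 = 3.5.
- Grade 3 rate: Section 1.5 lists Grade 3 AEs seen in more than 2 of 168 participants, and QT prolongation is not among them. If the list is complete, the rate is at most 2/168 = 1.2%.
- Product: 0.35 × 2/168 = 0.004; 3.5 × 2/168 = 0.04 participants.

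As a ceiling, the any-grade rates in Section 5.6 give 0.04 to 0.35 (17/168 = 10.1%) and 0.06 to 0.58 (37/223 = 16.6%). These overstate Grade 3 events.

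**With a cap, min(baseline + 30, 500):** 470 → 500 (unchanged); 471 → 500 (1 ms lower); 479 → 500 (9 ms lower); 480 → 500 (10 ms lower). The overlap is gone.

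**The case against.** The case for leaving the row alone has real force.

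- **The clauses are sequential and the second is permissive.** Dosing stops; later it *may* resume. An investigator who keeps holding at 505 ms breaks no rule.
- **Other conditions apply as well.** Section 5.6 sends the investigator to both its bullets and Table 2, so improvement and a judgment of safety are also needed. In Cycle 1, a QTcF still above 500 ms is hard to call reasonable resolution of a Grade 3 event.
- **A baseline-relative limit is coherent** for people whose QTcF is long to begin with, and the proposed cap moves it by only 1–9 ms for those eligible without PI approval. Baselines of 480 ms or more need individual PI approval.
- **The expected number affected is close to zero.**

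All of this stands and keeps the priority low. It does not supply the missing ceiling: every other condition is a matter of judgment, and the only figures for resumption are those in the row itself.

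Two stronger readings are tempting and are not supported. A reader might infer that a single QTcF value both triggers the hold and lifts it; the trigger requires at least two separate ECGs. A reader might also infer that the row authorises restarting ivosidenib above 500 ms, or flatly contradicts itself; because resumption is discretionary and the other conditions apply, the row only leaves open which clause governs in the band.

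**Conclusion.** The gap is real but narrow. For baselines of 471–479 ms the hold and release ranges overlap by 1–9 ms, and by 10 ms or more for PI-approved baselines of 480 ms or more. At 470 ms or below there is no overlap, and the Grade 2 row already allows 250 mg without interruption up to 500 ms.

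The estimate of 0.004 to 0.04 participants rests on three things: the assumed 1–10% share of long baselines, completeness of the Grade 3 list in Section 1.5 (its wording leaves some doubt), and an average Grade 3 risk in people with long baselines, who may be at higher risk. Against that, a Grade 3 event matters here only if QTcF lies in the narrow band when resumption is considered. The arithmetic of the overlap is certain; the head count is only indicative. This is a cheap improvement and not a necessary correction.

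**What to change.** In the Grade 3 row of Table 2, change the relative branch to *within 30 ms of baseline and no more than 500 ms*. Leave the sex-specific branch and exclusion 19 as they are. The 500 ms figure is the table's own boundary between Grades 2 and 3.

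The change is one clause, with no new visit, ECG or procedure, and can go in at the next amendment. The cost falls on participants with a baseline above 470 ms, who would have less than 30 ms of room: 500 − 479 = 21 ms at a baseline of 479, and 500 − 490 = 10 ms at a PI-approved 490. A PI-approved participant with a baseline above 500 ms could not resume even on returning to baseline. If the sponsor wants to keep that option, it should be written as an explicit exception.
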